### 17. Results and Data Sharing.

17A. Could this research generate any results that could be clinically relevant, including individual research results, or general, or aggregate research findings?

No  
 Yes, clinically relevant individual research results  
 Yes, clinically relevant general or aggregate research findings

17A1. If yes, explain what clinically relevant research results will be generated, whether they will be disclosed to subjects or others (e.g. subject's primary care physician), and if so, under what conditions. Address individual research results and/or general or aggregate research findings, as appropriate. *This also needs to be explained in the consent document.*

17B. For other research results, select all that apply:  Not Applicable

Overall study results will be shared directly with subjects  
 Individual results or incidental findings of individual subjects will be shared with subjects or others  
 Data will be submitted to a repository or database as part of data sharing agreement (e.g. genomic data sharing)

17B1. Explain your selection(s), including how the data or results will be shared and with who (e.g. subject's primary care physician, data repository).

**18. Local Context and Multi-Site Study.**

**18A.** Describe the locations of where the study team will obtain information or biospecimens through intervention or interaction with the subject or obtain the subjects' private identifiable information.

All aspects of the study will take place online Enrollment will take place via Zoom. All survey instances will also be administered through Zoom. For the intervention group, the study will be conducted online via a private encrypted, password protected Zoom video call.

**18B.** If the study will engage employees or agents of non-MSU organizations (e.g.  Not Applicable performance sites), explain how the employees or agents will be engaged (e.g. will they perform research procedures, will they obtain informed consent from subjects).

**18C.** If the study involves multiple performance sites, describe the methods for  Not Applicable communicating with engaged sites related to the protection of human subjects (e.g. any potential unanticipated problems that may involve risks to subjects others).

**18D.** If there are any cultural or local contexts or requirements that may impact the  Not Applicable protection of human subjects or present additional risks to subjects that have not otherwise been described, please describe. If research is conducted outside the state of Michigan, this could include additional state or international requirements or laws.

**18E.** If translations to a language other than English will be provided to subjects,  Not Applicable describe the translation process.

*CLICK IRB: Upload translated documents to the appropriate SmartForm page(s).*

**19. Resources and Financial Compensation and Costs.**

**19A.** If someone will receive a payment for recruiting the subjects, explain the amount of payment, who pays it, who receives it, and why they are being paid.

**19B.** If subjects will incur additional financial costs as a result of their participation  Not Applicable in this study, explain the additional costs.

**19C.** Describe any resources not otherwise described elsewhere in the submission (e.g. internal funding) for the protection of human subjects.

*CLICK IRB: Upload any funding materials not accessible in Kuali Coeus in the Supporting Documents SmartForm page.*

## HRP-503 - Template – Protocol

**19D.** If subject's biospecimens (even if identifiers are removed) may be used for commercial profit, describe whether the subject will or will not share in the commercial profit. *This also needs to be explained in the consent document.*

Not Applicable

### 20. Information and/or Biospecimen(s) Management and Confidentiality.

**20A.** Select the appropriate option:

Identifying or coded information will not be stored with the information and/or biospecimen(s)  
 Identifying or coded information will be stored with the information and/or biospecimen(s)

**20B.** Please explain your selection. If you are storing identifying or coded information with the information and/or biospecimen(s), explain why identifiable or coded information and/or biospecimen(s) needs to be maintained and how long it will be necessary to maintain it.

Identifying information from the initial survey will not be stored with other information from the study.

**20C.** Describe the procedures and safeguards you will use to secure the information and/or biospecimen(s), including during transport of information and/or biospecimen(s).

Only the project investigators and trained research assistants will be interacting with study participants or their data. When enrolling subjects, each subject will be assigned an identification number. The data itself will only be identified by these code numbers, making it impossible for anyone to link data to a person's name or any other identifying information. All de-identified data will be stored separately, away from identifiable forms (e.g., consent forms). Any electronic data files will be password-encrypted and stored on a password-protected computer.

**21. Drug and/or Device Storage, Handling, and Administration.**  Not Applicable

Describe the procedure and plan for storage, handling, and administration of the drug and/or device so that they will be used only on enrolled subjects and be used only by authorized study personnel.

### 22. Future Research.

If the research involves the collection of identifiable private information or identifiable biospecimens, select the appropriate option:

The subject's information or biospecimens, even if identifiers are removed, could be used for future research studies or distributed to another investigator for future research studies  
 The subject's information or biospecimens, even if identifiers are removed, will NOT be used or distributed for future research studies

*Please be sure to carefully consider the appropriate option, as this needs to be explained in the informed consent and can limit what is done or used for future research.*

**23. MSU Additional Information.**  Not Applicable

Identify if your study involves any of the following: (check all that apply)

Use of human stem cells  
 Research with biospecimens will (if known) or might include whole genome sequencing (i.e., sequencing of a human germline or somatic specimen with the intent to generate the genome or exome sequence of that specimen). *If so, this needs to be explained in the consent document.*

**Other Click IRB Document Uploads As Appropriate  
(Applicable to Expedited or Full Board Studies)**

- *Upload list of external study team members (non-MSU individuals) to the Study Team Members SmartForm page, Question 2.*
- *Upload other institution(s) approval letter(s), if submitted to other IRB(s) or ethics committees, to the Supporting Documents SmartForm page.*
- *Upload FDA communications, package inserts, FDA form 1572, or other information related to drugs or devices to the appropriate Drug or Device SmartForm pages.*
- *Upload the HRP-540 - Template - ICH-GCP - For Investigator to the MSU Additional Study Information SmartForm page.*
- *Upload HRP-541 - Template - Involvement of Prisoners in a Research Project to the MSU Additional Study Information SmartForm page.*
- *Upload the investigator brochure to the Supporting Documents SmartForm page*
- *Upload the MRI Screening Form – Women to the Supporting Documents SmartForm page.*
- *Upload the translation of instrument(s) provided to non-English speaking subjects to the Supporting Documents SmartForm page.*
- *Upload the curriculum vitae(s) when research is more than minimum risk to the Supporting Documents SmartForm page.*
- *Upload case report forms to the Supporting Documents SmartForm page.*
- *Upload the Non-MSU Employee Conflict of Interest Disclosure Form to the Supporting Documents SmartForm page.*
- *Upload any other pertinent documents related to the proposed research study to the Supporting Documents SmartForm page*

Clinical Trial Statistical Analysis Plan

Title: Effects of Open-label Placebos Administered Through Telehealth on COVID-related Stress, Anxiety, and Depression

Brief Title: Effects of Open-label Placebos on COVID-related Psychological Health

Study Sponsor: Michigan State University

Principle Investigator:

Name: [name]

Official Title: Professor of Psychology

Affiliation: Michigan State University

[contact]

Email: [contact]

NCT Number: NCT05035550

Version Date: 1.22.21

Statistical Analysis Plan

All analyses were conducted on SPSS version 26 (IBM, Armonk, NY). Prior to our primary analyses, we first interpolated missing data using a maximum likelihood estimation (MLE). Second, we conducted an independent sample t-test on baseline measures of each primary outcome measure to ensure that the control and open-label placebo group did not differ prior to the administration of the intervention.

The primary outcomes at the endpoint (reduction in COVID stress, perceived stress, anxiety, and depression) were calculated using change from baseline scores (endpoint minus baseline) with positive numbers indicating greater reduction in symptoms at endpoint. First, each primary outcome was submitted to a one-way analysis of covariance (ANCOVA), with group as the independent variable and the mean baseline score for each outcome measure submitted as a covariate to control for variability in baseline scores (Lembo et al., 2021; Van Breukelen, 2006). We reported outlier detection procedures and additional robust analyses in the Supplementary Materials. Effect sizes for pairwise comparisons were calculated using Cohen's d. Secondary outcomes were analyzed using descriptive statistics and t-tests. All significance tests were analyzed at $p = .05$.

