**4. Reasonably Foreseeable Risks.**

**4A.** There are (select one of the following):

- No reasonably foreseeable risks to subjects
- Reasonably foreseeable risks to subjects

**4B.** Explain the selection. *If you selected that there are reasonably foreseeable risks to subjects, describe the risks, considering physical, psychological, social, legal and economic risks.*

We expect the risk to subjects to be minimal. There is a small risk of psychological distress from replying to questions regarding their psychological and physical health within the COVID-19 pandemic context. Participants in the intervention conditions who are not accustomed to taking pills may also experience distress from taking inactive placebo pills

**4C.** If you selected that there are reasonably foreseeable risks, describe the procedures for protecting against or minimizing potential risks and provide an assessment of their likely effectiveness.

In order to protect subjects from the risk of psychological distress from replying to questions regarding their psychological and physical health within the COVID-19 pandemic context, participants will have the option to skip any questions or withdraw from the study at anytime. Participants in the intervention conditions will be asked if they are willing to take placebo pills, and those who are not comfortable or wishes not to do so will not be able asked to participate in the study. Moreover, participants will receive resources, which can provide additional support and counseling if needed.

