Our assumption of a d effect size of .60 is a liberal assumption based on the literature in which the d effect size between a non-deceptive placebo and a no treatment control ranges from .30 to 1.00. The most relevant non-deceptive placebo study is El Brihi et al. (2019) in which they tested the effects of non-deceptive placebos on emotional distress and positive mental well-being. Comparing two types of non-deceptive placebos versus a control showed a non-deceptive placebo effect that ranges from a Cohen's d of .78 to 1.01 on emotional distress. Comparing two types of non-deceptive placebos versus a control showed a non-deceptive placebo effect that ranges from a Cohen's d of .55 to .93 for psychological well-being. As such, we estimate that a d effect size of .60 between a control group and our non-deceptive placebo group because our primary outcomes is also emotional distress and psychological well-being. A .60 d effect size is within a reasonable range of what is expected regarding a non-deceptive placebo effect on emotional distress. This will allow us to run approximately 50 in each condition, which is more than the sample size of the El Brihi et al. (2019) study in which they had n = 29 in the control condition and n = 30 and n = 31 in each of the non-deceptive placebo condition.

For our primary outcomes, we plan to run a 2 (Group) by 3 (Time: Time 2, Time 3) mixed factorial ANOVA (while controlling for baseline levels) followed by independent pairwise comparisons at each of time point. When possible, we plan to use multiple imputation methods to account for missing data. If a participant is missing data from 2 or more time points for our primary outcome, they will be removed for analyses. If a person is unresponsive for 5 days, we will consider them a dropout. We will send a final letter indicating that we apologize for their drop

and that they can contact us if they need anything and provide them resources if they require it. If participants wants to drop out, we can inquire why and offer them resources and contact information for future studies.

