Again, we also only have a budget to run 50 participants in each condition. We plan to apply for further funding but for now, this is our limit. We want the option to test more than 50 in each condition because it will increase our confidence in any effect we find. If we receive funding, we will run more than 50 in each condition, but we will not enroll more than 200 participants in each arm. The 200 in each arm maximum will allow us to detect a d effect size of .30 with some room for error such as participants dropping out or not filling out all of our measures.

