## HRP-503 - Template – Protocol

If there are any anticipated circumstances where the researcher will withdraw subjects from the study regardless of the subject's wishes, describe the circumstances and the procedures when subjects are withdrawn from the study.

The participant will take a total of 4 surveys spanning 17 to 20 days. It is very important that participants take the first two surveys and the last survey (First, Second, and Fourth) or they will not be able to proceed with the study. The first two surveys help us establish baseline psychological and physical health and if they do not take it, we will not be able to do anything meaningful with the rest of their data. They really can only miss the Third Survey.

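### Missing values are filled once by maximum likelihood and then analysed as if observed; this harms the primary ANCOVA only if whole Fourth Survey scores were filled

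*SAP*

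**What the plan says.** The SAP puts the missing-data step before everything else: "we first interpolated missing data using a maximum likelihood estimation (MLE"). A baseline t-test follows, and then "each primary outcome was submitted to a one-way analysis of covariance (ANCOVA), with group as the independent variable" and the baseline score as covariate. The outcome is the change between baseline and endpoint. Secondary outcomes get descriptive statistics and t-tests. The SAP does not say which values were filled, whether group was in the fill-in model, how many completed datasets there were, or how standard errors allowed for the filling.

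Protocol section 9Bii has a different method in mind: "When possible, we plan to use multiple imputation methods to account for missing data". It also sets two rules on incomplete participants: "If a participant is missing data from 2 or more time points for our primary outcome, they will be removed for analyses", and "If a person is unresponsive for 5 days, we will consider them a dropout". Section 15 requires the First, Second and Fourth Surveys and says of participants: "They really can only miss the Third Survey". Section 4C adds that "participants will have the option to skip any questions or withdraw from the study at anytime". The upper sample size in section 9Bii is justified "with some room for error such as participants dropping out or not filling out all of our measures", with no rate given.

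**The concern.** A maximum-likelihood fill-in replaces each missing value with its prediction. An ordinary ANCOVA then counts that prediction as a full observation that happens to lie on the fitted line. Sample size is overstated and residual scatter understated, so with group in the fill-in model the standard error is too small and false positives rise. With group left out, filled participants in both arms are predicted from the same equation, which pulls the estimated difference toward zero.

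The primary outcome uses the endpoint directly, so a filled Fourth Survey score goes straight into the main test. Section 9Bii leaves room for this: someone who completed the Third Survey but not the Fourth is missing one time point, stays in, and needs a filled endpoint. Section 15 suggests that such a person would not be in the analysis. As written, a reader cannot tell which applies.

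**Working it through.** **Inputs.** From the documents: two arms, a minimum of 50 per arm, d = 0.60 and alpha 0.05 (section 9Bii); ANCOVA of endpoint change on group and baseline (SAP). Assumed: a two-sided test, endpoint = Fourth Survey, complete baseline scores, endpoints missing completely at random in both arms, a missing share m of 5%, 10% or 20% (5, 10 or 20 of 100 participants), and the correlations shown below. The plan states no figure for missing data, so there is none to reproduce; 50 per arm is taken as given.

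**Group and baseline in the fill-in model.** Filled points lie on the line fitted to the n(1−m) observed cases, so the group estimate is unchanged.
- True SE is proportional to σ/√(n(1−m)).
- The residual sum of squares is still about σ²n(1−m), but it is divided by about n, so reported SE is proportional to σ√(1−m)/√n.
- Reported SE / true SE ≈ √(1−m) × √(1−m) = 1−m.
- Type I error ≈ 2[1 − Φ(1.96(1−m))].

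m = 5%: 1.96 × 0.95 = 1.862, giving 6.3%. m = 10%: 1.764, giving 7.8%. m = 20%: 1.568, giving 11.7%. Simulation (8,000 null runs, correlations 0.5) gives 6.4%, 7.5% and 11.9%. By the formula, type I error passes 6% at about 4 filled endpoints per 100 and 10% at about 16.

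**Third Survey added.** A participant kept under section 9Bii without a Fourth Survey has a Third, so the fill-in may use it. Ranges below span separate simulation runs.

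| Fill-in model, group included | 5% | 10% | 20% |
|---|---|---|---|
| Baseline and group (formula) | 6.3% | 7.8% | 11.7% |
| Third Survey added, all correlations 0.5 | 6.0–6.3% | 7.2–7.6% | about 11% |
| Third Survey added, Third–Fourth 0.8, others 0.6 | about 5.7% | 6.1–6.6% | 8.2–8.8% |

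In the last row, reported/true SE is about 0.97, 0.94–0.95 and 0.87–0.89. Adding random noise to a single fill-in does not cure the problem: with baseline and group only, type I error is 7.5% and 10.6% at 10% and 20%.

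**Group left out.** With baseline only, the effect is multiplied by about 1−m: 0.60 × 0.95 = 0.57, 0.60 × 0.90 = 0.54, 0.60 × 0.80 = 0.48. Simulation gives 0.57, 0.53 and 0.48 (mean difference in units of the complete-data SD). With the Third Survey used, it is about 0.58–0.60, 0.56–0.59 and 0.52–0.57. Type I error stays near 5%.

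**Only skipped items filled.** Assuming 7 to 20 items, inter-item correlation 0.35 and 2–5% of items skipped, a true 0.60 is estimated as 0.592–0.601, with type I error 4.7–5.7%. That is no detectable harm.

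**Only Third Survey scores filled.** The SAP's primary ANCOVA does not use them, so nothing changes. This would not carry over to the repeated-measures ANOVA in section 9Bii or to a secondary t-test on Third Survey scores.

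**Pooled multiple imputation** (20 imputations, group in the model, Rubin's rules). Type I error is 5.1–5.7% at 5–20% missing in one set of runs and 4.8–4.9% at 10% and 20% in another. In the latter, the mean estimate of a true 0.60 is 0.60.

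**The case against.** The strongest reply is that no harm to the primary result is shown. The only gaps that the protocol expressly allows are skipped questions and a missed Third Survey, and both are harmless here. To need a filled endpoint, a participant must complete the Third Survey, miss the Fourth, and be kept despite section 15 and the 5-day dropout rule. The removal rule in section 9Bii also fits section 15 if the one tolerated gap is always the Third Survey. All of this stands, and it makes the point conditional. It does not close it: the removal rule as worded keeps a participant who lacks only the Fourth Survey, and nothing says whether dropouts are analysed.

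It can also be said that the harm is small in the mildest settings. That stands too: with group in the model and a strongly correlated Third Survey, the excess at 5% missing is about 0.7 percentage points, and with group left out the error rate is not inflated at all.

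A further reply is that the SAP is short, is written after the analyses, and points to robust analyses in Supplementary Materials. Those materials are not among the documents, so they can be neither counted as a correction nor ruled out. Direct likelihood estimation would avoid the problem, but interpolating data and then running t-tests and ANCOVA does not read that way.

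A reader might infer that the SAP contradicts the protocol by dropping multiple imputation. The protocol's promise is qualified by when possible, so there is a change of method without a stated reason, but no strict contradiction.

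**Conclusion.** The concern holds in conditional form. The analysis as described treats filled values as observed. If whole Fourth Survey scores were filled, the primary ANCOVA is either over-precise (group in the model) or its effect is shrunk (group left out), by the amounts shown in the check. If none was filled, the primary result is essentially unaffected.

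A reader might infer that the trial's false-positive rate is 11–12%, or that dropouts' endpoints were in fact filled. The documents support neither. The first needs about 20 of 100 endpoints filled, group in the model and no strongly correlated Third Survey; the second is permitted by one protocol rule and apparently excluded by another. Every size rests on assumed missing rates and correlations and on missingness completely at random. If missingness depends on unobserved outcomes, neither the fill-in nor the remedy below is guaranteed to be valid.

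**What to change.** - For the primary ANCOVA, use multiple imputation (for example, 20 or more imputations) with group, baseline, Third and Fourth Survey scores in the model, fit the ANCOVA in each completed dataset, and pool by Rubin's rules. Alternatively, fit a likelihood mixed model to the observed surveys with no fill-in.
- Keep the maximum-likelihood fill-in as a sensitivity analysis. State its model, including whether group was in it, and whether it worked on items or whole scores.
- Report missing counts by arm and survey, separating skipped items from whole missing surveys. If no Fourth Survey score was filled, say so; the primary result then stands essentially unchanged.
- Reconcile the removal and dropout rules in section 9Bii with section 15, so that the analysed participants are defined.

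The cost is SAP wording, one table and a small re-analysis of existing data. Intervals widen when endpoints are missing. Mean pooled SE against fill-in SE is 0.178/0.169 and 0.183/0.166 at 5% and 10% missing with correlations 0.5 (about 5% and 10% wider). With the Third–Fourth correlation at 0.8 and the others at 0.6, it is 0.163/0.158 and 0.166/0.156 (about 3% and 6% wider). That width reflects information that was not collected.

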**9B. Sample Size.**

**9Bi.** Provide an estimated sample size for the lifetime of the study at this investigator's sites.

100 to 400

**9Bii.** Describe the basis for that estimate.

We plan to screen as many as participants as possible that would allow us to enroll a minimum of 100 participants in a two-arm randomized controlled trial. Each arm will require a minimum of 50 participants. We determined this sample size in a few ways. One, the typical sample size for a between-subjects study comparing non-deceptive placebos to a control group ranges from 30 to 50 per condition (Kaptchuk et al., 2010; El Brihi et al., 2019; Locher et al., 2017). Two, from a more practical standpoint, we only have the financial resources to run approximately 50 in each condition. We are applying for additional funding, but for now, we only have a budget for 50 in each condition. Three, we determined 50 participants in each arm by hypothesizing a d effect size of .60 between the control group and each of the treatment arms with a power of .80 at an alpha level of .05. Non-deceptive placebo studies have typically used an ANOVA model followed up by pairwise comparisons. These effect sizes are calculated from these pairwise comparisons.

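### Secondary outcomes are tested by t-test with no baseline covariate; any that have a baseline value would be estimated more precisely by the ANCOVA already used for the primaries

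*SAP*

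**What the plan says.** The SAP defines four primary outcomes: "reduction in COVID stress, perceived stress, anxiety, and depression". Each is expressed as change from baseline and analysed by ANCOVA, with "the mean baseline score for each outcome measure submitted as a covariate to control for variability in baseline scores". For all other outcomes the whole provision is: "Secondary outcomes were analyzed using descriptive statistics and t-tests". It names no covariate, and it does not list the secondary outcomes, their time points or the score to be tested.

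The SAP mentions baseline measurements only for the primaries: "we conducted an independent sample t-test on baseline measures of each primary outcome measure".

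On data collection, Protocol section 15 (Withdrawal of Subjects) describes four surveys and says: "The first two surveys help us establish baseline psychological and physical health". It lists no instruments.

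**The concern.** The SAP adjusts for baseline where it matters most and gives a reason, namely variability in baseline scores. The same reason applies to any secondary outcome that was also measured at baseline, yet the SAP switches to a plain t-test there without explanation. The baseline surveys appear wider than the primaries: all four primaries are psychological, while the surveys also cover physical health.

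At stake are wider intervals and lower power for those secondary outcomes than the collected data would allow. Protocol section 9Bii says the current budget covers only about 50 per arm, so unused precision cannot readily be made up with more participants. Primary and secondary effects would also be reported on different footings, one conditional on baseline and the other not.

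**Working it through.** **Inputs from the documents**
- Minimum of 50 per arm, two arms (Protocol 9Bii).
- Planning effect d = .60, "with a power of .80 at an alpha level of .05" (Protocol 9Bii).
- Significance level .05 (SAP).

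**Assumptions, not in the documents**
- Two-sided tests.
- Baseline-endpoint correlation r of .3, .5 or .7.
- Equal SD at baseline and endpoint, with d expressed in endpoint SDs.
- The planning d applied to secondary outcomes, for which the documents state no effect size or power target.

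**Step 1. The plan's own figure.** For d = .60, power .80 and two-sided .05, the two-sample t calculation gives 44.6, so 45 per arm (44 by the normal approximation). The stated 50 is slightly generous: at 50 per arm, power is .84. The point below therefore does not depend on the trial being too small.

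**Step 2. Variance of the treatment effect, relative to an endpoint t-test**
- Endpoint t-test: 1
- Change-score t-test: 2(1 − r)
- ANCOVA on own baseline: 1 − r²
- ANCOVA relative to the change-score t-test: (1 − r²) / [2(1 − r)] = (1 + r)/2

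| r | ANCOVA ÷ endpoint t-test | Reduction | ANCOVA ÷ change-score t-test | Reduction |
|---|---|---|---|---|
| .3 | 1 − .09 = .91 | 9% | 1.3/2 = .65 | 35% |
| .5 | 1 − .25 = .75 | 25% | 1.5/2 = .75 | 25% |
| .7 | 1 − .49 = .51 | 49% | 1.7/2 = .85 | 15% |

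The two reductions run in opposite directions as r rises, so the size of the loss depends on which score the t-test uses. For every r in this range ANCOVA has the smaller variance under both readings.

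Against the endpoint t-test, ANCOVA with 50 per arm is worth 50/(1 − r²) per arm: 50/.91 = 55, 50/.75 = 67 and 50/.51 = 98.

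**Step 3. Power at 50 per arm, d = .60** (noncentral t with noncentrality = standardised effect × √(50/2) = standardised effect × 5; 98 degrees of freedom for a t-test, 97 for ANCOVA)
- Endpoint t-test: effect .60, noncentrality 3.00, power .84 at any r.
- Change-score t-test: effect .60/√[2(1 − r)] = .507, .600, .775.
- ANCOVA: effect .60/√(1 − r²) = .629, .693, .840.

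| r | Endpoint t-test | Change-score t-test | ANCOVA |
|---|---|---|---|
| .3 | .84 | .71 | .88 |
| .5 | .84 | .84 | .93 |
| .7 | .84 | .97 | .99 |

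**Step 4. A smaller effect.** At d = .30, the low end of the range the protocol cites, the endpoint t-test has power .32 and ANCOVA has .34, .40 and .55 at r = .3, .5 and .7.

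**Step 5. The condition.** All of this requires the outcome to have its own baseline value. Without one there is no such covariate, and the gain is zero.

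**The case against.** The strongest reply is that no secondary outcome is known to have a baseline value. The SAP ties baseline measures to the primaries only, and Protocol section 15 does not link the survey content to secondary outcomes. They could be ratings made only after the intervention, for which a t-test is the natural choice. This stands, and it is why the point is conditional. A reader might infer that the plan throws away baseline data on every secondary outcome; the documents do not show that.

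A reader might also take psychological well-being as a concrete example. Protocol 9Bii says "our primary outcomes is also emotional distress and psychological well-being", and well-being is absent from the SAP's four primaries. But it may have been dropped rather than made secondary. Those sections show a mismatch in the outcome list, not how well-being would be analysed.

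Third, calling the t-tests unadjusted goes beyond the text. The SAP scores its primaries as change from baseline, so the t-tests may use change scores too, and these already draw on baseline. This stands as to wording, and at r = .7 it shrinks the power gain to .97 versus .99. It does not remove the point, because ANCOVA has the smaller variance under either reading.

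Finally, the arms are randomised, so a t-test is valid. Chance baseline imbalance is random error already covered by the standard error, not bias. That stands in full. Using different methods for primary and secondary outcomes is not in itself an error.

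**Conclusion.** The point holds in conditional form and at low severity. The SAP names no baseline covariate for secondary outcomes, although it uses one for the primaries and baseline surveys exist. For any secondary outcome with a baseline value, the t-test gives up precision that ANCOVA would recover at almost no cost. The amount rests on an assumed r and on which score is tested. Against an endpoint t-test it is slight at r = .3 and substantial at r = .7; against a change-score t-test the order is reversed. The documents do not support a claim of bias, of an invalid test, or of precision lost on every secondary outcome. They leave undefined which outcomes are secondary, which have baseline values, and what score is tested.

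**What to change.** List the secondary outcomes with their time points, mark those measured at baseline, and state the score to be tested. Then replace the secondary-outcome sentence in the SAP with:

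*Each secondary outcome measured at baseline is analysed with the same ANCOVA as the primary outcomes (group, own baseline as covariate); t-tests are used only for outcomes first measured after baseline.*

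The replacement costs one sentence and one degree of freedom per model (97 instead of 98 at 50 per arm), and needs no new data. If no secondary outcome turns out to have a baseline value, the sentence changes nothing in the analysis.
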